7.2 Handling of Dropouts or Missing Data

7.2.1 Handling of Incomplete Dates for Adverse Events

Imputation rules for missing or partial AE start date are defined as follows.

If only day of AE start date is missing, - if the start date has month and year but day is missing, the first day of the month will be imputed. If this date is earlier than the first dose date, then the

first dose date will be used instead. If this date is later than the stop date (possibly imputed), then the stop date will be used instead.

If day and month of AE start date are missing - if the start date has year but day and month are missing, the first of January will be imputed. If this date is earlier than the first dose date, then the first dose date will be used instead. If this date is later than the stop date (possibly imputed), then the stop date will be used instead.

If the year of AE start date is missing or AE start date is completely missing, then Data Management will query site with no imputation and compare the full (or partial) AE end date to the first dose date. If the AE end date is before the first dose date, then the AE should be considered a pre-treatment AE. Otherwise, the AE will be considered a TEAE.

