#### Protocol VK-2019-001

#### Version 9.0, 15-October-2019

### Table 1: Schedule of Events in Phase 1 Dose Escalation

Assessment 	Screening	Сус	le 1	Cycle 2		Cycle 3 and Odd Cycles 	Cycle 4 and Even Cycles 	ЕОТ	Safety FU	LTFU
	Within 28 days of C1D0	Day 0	Day 14 (± 1 d)	Day 0 (+3 d)	Day 14 (± 3 d)	Day 0 (± 3 d)	Day 0 (± 3 d)	7 d $(\pm 3 d)$	$28 d (\pm 7 d)$	q12 w $(\pm 1 w)$ post-last dose
Informed consent	X		$(\pm 1 \text{ u})$	(+5 u)	(± 5 u)	(± 5 u)	(= 5 u)	post lust dose	post lust dose	post lust dobe
Medical/Oncology History	Х									
ECOG Performance Status 	X	$X^{10}$						Х		
Vital Signs 	Х	Х	Х	Х	Х	X	Х	Х	Х	
Height & Weight 	Х	$X^{10}$		$X^{10}$		$X^{10}$	X 	Х	Х	
Physical Examination 	X	$X^{10}$		$X^{10}$		X 	X 	Х	Х	
Hematology Labs 	Х	$X^{10}$	Х	$\mathrm{X}^{10}$	Х	$\mathrm{X}^{10}$	$\mathrm{X}^{10}$	Х	Х	
Chemistry Labs 	X	$X^{10}$	Х	$X^{10}$	Х	$X^{10}$	$X^{10}$	Х	Х	
Urinalysis 	X	X 		$X^{10}$		$X^{10}$	$X^{10}$	Х	Х	
Coagulation Panel 	Х	$X^{10}$		$X^{10}$		$X^{10}$	$X^{10}$	Х	Х	
Pregnancy Test 	X	X 		$X^{6,10}$		X 	$X^{6,10}$	Х	$X^{6,10}$	
Triplicate ECG 	X	Х	Х	Х				Х	Х	
Adverse Events	Х	Х	Х	Х	Х	Х	Х	Х	Х	
Concomitant Medications	Х	Х	Х	Х	Х	Х	Х	Х	Х	
VK-2019 	X									
PK Plasma 		Х	Х	Х		X (C3 only)				
Plasma EBV DNA 	X		Х	Х	Х	X (C3 only)		Х		
Tumor Assessments 	X					X 		X 		X 
Survival										$X^{14}$

Protocol VK-2019-001

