## **Reporting Period**

For AEs (including SAEs), the active reporting period to the sponsor or its designated representative begins from the time the patient provides informed consent, which is obtained prior to the patient's participation in the study, i.e., prior to undergoing any study-related procedure and/or receiving investigational product, until either a) 28 calendar days after the last administration of the investigational product, or b) initiation of a new anti-cancer therapy. Should an investigator be made aware of any SAE considered at least possibly related to study drug occurring any time after the active reporting period, it must be promptly reported. Confidential Worsening of signs and symptoms of the malignancy under study should be reported as AEs in the appropriate section of the CRF. Disease progression assessed by measurement of malignant lesions on radiographs or other methods should not be reported as adverse events.

An adverse reaction is defined as any AE caused by the use of a drug. Adverse reactions are a subset of all suspected adverse reactions, for which there is reason to conclude that the drug caused the event. Examples of adverse reactions include but are not limited to:

- Abnormal test findings;
- Clinically significant symptoms and signs;
- Changes in physical examination findings;
- Hypersensitivity;
- Drug abuse;
- Drug dependency.

Additionally, they may include the signs or symptoms resulting from:

- Drug overdose;
- Drug withdrawal;
- Drug misuse;
- Drug interactions;
- Exposure during pregnancy;
- Exposure via breastfeeding;
- Medication error.

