7 STATISTICAL ANALYSES

7.1 General Methods

The statistical analysis will be conducted following the principles specified in the International Conference on Harmonisation (ICH) Topic E9 Statistical Principles for Clinical Trials (CPMP/ICH/363/96).

All statistical tabulations and analyses will be done using SAS®, Version 9.4 or higher.

Unless otherwise noted, continuous variables will be summarized using number of non-missing observations (n), arithmetic mean (mean), standard deviation (SD), median, minimum, and maximum; categorical variables will be summarized using the frequency count and the percentage of subjects in each category.

In the data listings, study day relative to first dose of study drug may be presented. Study day relative to first dose will be calculated as: event date – first dose date in the study (+ 1 if event date \geq first dose date in the study).

When appropriate, baseline is defined as the last non-missing result with a collection date-time less than the date-time of the first dose of study medication. If time is missing, unless otherwise specified, baseline is the last non-missing result prior to or equal to the date of first dose of study drug.

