7.14.1 Adverse Events

Adverse events will be listed, including the verbatim description and MedDRA preferred term and system organ class (SOC).

Treatment emergent adverse events (TEAEs) are defined as those starts or severity becomes worse after the first dose of study treatment.

TEAE leading to study treatment discontinuation and death will be summarized by SOC, by preferred term and by maximum CTCAE grade (according to NCI CTCAE Version 5.0). The incidence of TEAEs will be based on the numbers and percentages of patients with events and number of events. In addition summary of DLT will also be provided for first cycle.

TEAE data will be presented across all cycles and for each cycle. The denominator for each cycle will be the number of patients available at the start of the cycle who received at least 1 dose of study drug for that cycle.

Individual patient listings will be prepared for AE leading to study treatment discontinuation and death. Listing of the first cycle DLTs for each cohort will be provided.

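### SAP 7.2.1 moves a partial AE start date to the first-dose date even when the recorded month or year lies wholly before dosing

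*SAP*

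**What the plan says.** SAP 7.2.1 has two branches for partial AE start dates. If only the day is missing, the start is set to the first of the recorded month; if day and month are missing, to 1 January of the recorded year. Both branches then apply the same two adjustments in turn:

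- A floor: "If this date is earlier than the first dose date, then the first dose date will be used instead".
- A cap: "If this date is later than the stop date (possibly imputed), then the stop date will be used instead".

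A third branch, for a start with no year, does not impute. It classes the AE as pre-treatment if it ended before first dose and as treatment-emergent otherwise.

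SAP 7.14.1 describes treatment-emergent AEs (TEAEs) as "defined as those starts or severity becomes worse after the first dose of study treatment". On study day, SAP 7.1 says: "In the data listings, study day relative to first dose of study drug may be presented". Its formula makes the first-dose date Day 1.

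Pre-dose AEs are in the data. Under the Protocol's Reporting Period section, AE collection "begins from the time the patient provides informed consent", and Table 1 puts consent at screening, "Within 28 days of C1D0".

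**The concern.** A first-dose floor is a sensible conservative choice when a partial date leaves it open whether onset came before or after dosing. Here it also applies where the record has already settled the matter: a month or year that ended before first dose proves pre-dose onset, and the rule overwrites that.

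The SAP's TEAE definition has a separate limb for AEs that worsen after dosing, which is how an AE already present at baseline can qualify. The floor can bypass that limb by making such an AE look newly started.

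SAP 7.2.2 does not treat medications this way. A medication start with a missing day goes to the first of the month with no first-dose floor. A drug given for the AE in the example below, and also dated only to May, would be placed at 1 May, 40 days before the AE's imputed onset of 10 June.

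At stake are the analysis onset date of such AEs and possibly their treatment-emergent status. AE frequency is part of the Phase 1 primary endpoint (SAP 4.1), so the classification should be right even where few records are involved.

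**Working it through.** The plan states no figure for this rule, so there is nothing to reproduce. The check applies the rule literally to test dates.

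**Inputs.** Imputation, floor and cap from SAP 7.2.1. Study day from SAP 7.1: event date minus first-dose date, plus 1 if the event is on or after first dose. All calendar dates below are assumptions.

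| Case | Recorded start | Start under SAP 7.2.1 | Study day | What the record shows |
|---|---|---|---|---|
| A. First dose 10 June, AE present at dosing | May | 1 May, floored to 10 June | 0 + 1 = 1 | 31 May or earlier: Day -10 or earlier |
| B. First dose 10 June, AE stopped 5 June | May | 1 May, floored to 10 June, capped to 5 June | -5 | 31 May or earlier: Day -10 or earlier |
| C. First dose 13 January 2020, AE present at dosing | 2019 | 1 January 2019, floored to 13 January 2020 | 0 + 1 = 1 | 31 December 2019 or earlier: Day -13 or earlier |
| D. First dose 10 June, AE present at dosing | June | 1 June, floored to 10 June | 0 + 1 = 1 | Before or after dosing: ambiguous |

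Cases A and C are the error. In case B the cap keeps the AE pre-treatment, but the start becomes the stop date. That rescue needs a complete stop date: the cap refers to a stop date that may itself be imputed, yet the SAP gives no imputation rule for partial AE stop dates. Case D is where the floor does its proper job.

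**How early could onset be?** In case A only the upper limit (Day -10) is certain. A lower limit of Day -28 (13 May) holds only if onset followed consent and consent fell inside the 28-day window.

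**Can such records occur?** If screening used the full 28 days, it would reach the previous calendar month for every first-dose date except the 29th to 31st of a month. There are 29 such dates in a non-leap year, so 365 - 29 = 336 of 365 (92%). It would reach the previous calendar year for 1 to 28 January, 28 of 365 (8%). Shorter screening lowers both shares. These are shares of possible dosing dates, not rates of affected AEs; the documents give no rate of partial dates.

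**Effect on a percentage.** If the AE is counted in a Cycle 1 row, and the patient is not already in that row, the row rises by 1/n: 1/3 = 33.3 points, 1/6 = 16.7 points, 1/16 = 6.3 points.

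**The repaired rule on the same dates.**

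- Case A: consent on 13, 20 or 27 May gives a start on that date, Day -28, -21 or -14. Removing the floor with no consent limit would give 1 May, Day -40.
- Case C: consent on 16 December 2019 gives Day -28. With no consent limit the start would be 1 January 2019, Day -377.
- Case D: unchanged at Day 1.

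**The case against.** The strongest case against is that no changed result has been shown. Much of it stands.

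- **Treatment-emergent status.** A reader might infer that every such AE becomes a TEAE. The definition speaks of onset after the first dose and does not say how onset on the first-dose date is treated. The third branch of SAP 7.2.1 points towards counting it, but that is inference.
- **Tables.** A reader might infer that overall TEAE incidence is inflated. The SAP's organ-class, preferred-term and grade tables are narrow: "TEAE leading to study treatment discontinuation and death will be summarized by SOC". A pre-dose AE that turns fatal has worsened and is a TEAE anyway. The later sentence, "TEAE data will be presented across all cycles and for each cycle", may cover only that same subset. SAP 7.14 does name AE incidence generally as an endpoint, so the wider reading is possible but not established.
- **Listings.** Study day is optional, and nothing says that listings show imputed rather than recorded dates. If recorded dates appear, the reader still sees May.
- **Size of the date error.** A reader might take Day -28 as a firm bound. The reporting period limits collection, not onset, and Table 1, footnote 16, tolerates some out-of-window visits.
- **Duration.** A reader might infer biased AE durations. SAP 4.1 names duration, but SAP 7.14.1 specifies no duration summary.
- **Mitigation.** The Protocol's Quality Control section has missing data queried at site, and the SAP serves only an abbreviated CSR. The error also runs in the conservative direction.

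None of this removes the defect. Imputation rules exist for what queries leave unresolved. The third branch is conservative because it has no start year to work with; here the recorded month or year answers the question.

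**Conclusion.** The rule is wrong as written; severity minor. What follows from the text alone is that an AE present at dosing, with a recorded start month or year wholly before first dose, gets an analysis onset of Study Day 1. That the defect exists is certain; its consequences are conditional:

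- it becomes a TEAE only if onset on the first-dose date counts as after first dose;
- a listing misleads only if imputed dates or study days are displayed;
- a by-cycle percentage moves, by the 1/n amounts shown, only if that presentation covers the AE.

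The number of affected AEs cannot be computed and is probably small. Dose escalation and the MTD do not depend on this rule: the Safety Review Committee decides cohort by cohort under Protocol section 6, and a DLT must be at least possibly related to VK-2019.

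**What to change.** Amend SAP 7.2.1 as follows.

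- Apply the first-dose floor only when the recorded month and year (or the year, if only that is known) equal those of first dose.
- If they are earlier, class the AE as pre-treatment unless its severity worsens after dosing. Impute its start as the first day of the recorded month (or year), or as the informed-consent date if consent falls later within that month (or year), capped at the stop date.
- State that an onset imputed to the first-dose date counts as a TEAE.

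The consent limit prevents the opposite error, an onset placed implausibly early. Ambiguous dates keep their present conservative handling.

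Cost: two or three sentences in the SAP, with no protocol change, no new data and no new output.

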7.2.2 Handling Missing or Partial Prior and Concomitant Medication Dates

For a missing or partial medication start date, if only Day is missing, the first day of the month will be assumed. If day and month are both missing, the first day of the year will be assumed. If day, month and year are all missing, the date before the first dose date will be assumed.

For a missing or partial medication stop date, if only day is missing, the last day of the month will be assumed. If day and month are both missing, the last day of the year will be assumed. If day, month and year are all missing, 'continuing' status to stop date will be assigned.

7.3 Study Population

- All Enrolled Population: All subjects who sign informed consent form and were confirmed eligible and assigned to a treatment cohort.
- All Treated Population (Safety Population): All subjects who receive at least one dose of VK-2019. All Treated Population will be used for the summaries of demographics, baseline characteristics, prior therapy, prior history, and safety.
- PK Population: All subjects who receive at least one dose of study medication and have available VK-2019 plasma concentration data.
- Response Evaluable Population: All treated subjects with measurable disease at baseline and one of the following: 1) at least one post-dose tumor assessment, 2) discontinuation prior to the first efficacy assessment due to clinical disease progression or toxicity or 3) death either on treatment or within 28 days of last VK-2019 dose.

• EBV DNA Population: All subjects who receive at least one dose of study medication and have available biomarker data.

7.4 Subject Accountability

Summaries of analysis populations and subject disposition will be presented by cohort and will contain the following information:

- Number of subjects enrolled
- Number and percent of subjects who were dosed
- Number and percent of subjects who discontinued early from the study and reason for early discontinuation
- Number and percent of subjects who discontinued treatment and reason for discontinuation
- Number and percent of subjects in the All Treated Population, Response Evaluable Population and EBV DNA Population
- Number and percent of subjects entered in safety and long term follow-up

This table will be based on All Enrolled Population.

Subject disposition listing will be provided for All Enrolled Population.

7.5 Protocol Deviation Reporting

No TLF's will be provided for abbreviated CSR.

7.6 Demographics Characteristics

A listing will be provided for demographics characteristics for All Treated Population, including patient age, sex, race, ethnicity, height and weight at baseline, etc.,

7.7 Medical and Surgical History

Medical and surgical history will be coded using the Medical Dictionary for Regulatory Activities (MedDRA, Version 23.0 or later) and listed for All Treated Subjects by SOC and PT.

7.8 Prior and Concomitant Medications

Prior medications are defined as those medications that started and stopped prior to the first dose of study drug. Concomitant medications are defined as all medications received during the

treatment period, that is, those medications with a start date on or after the first dose of study drug (inclusive) and before last dose of study drug (inclusive), or started prior to the first dose of study drug and were continued after the first dose of study drug.

Prior and concomitant medications will be coded using the World Health Organization Drug Dictionary (WHODDE – global March 20 B3 version) and classified according to anatomical therapeutic chemical code levels. Prior and concomitant medication data will be listed by ATC classifications level and preferred term for All Treated Population.

7.9 Extent of Exposure

The extent of exposure will be characterized according to the duration of exposure, the total number of cycles administered and the median (range) of cycles administered. Descriptive statistics of cumulative dose and dose intensity will also be presented for All Treated Population. A listing will also be provided.

7.10 Analysis of Pharmacokinetic Data

The PK concentration population is defined as all enrolled patients treated who have at least one concentration evaluation. The PK parameter analysis population is defined as all enrolled patients treated who have at least one of the PK parameters of interest.

Standard plasma pharmacokinetic parameters including the maximum plasma concentration (C_{max}) and area under the plasma concentration versus time curve (AUC) for VK-2019 will be estimated using non-compartmental analysis. If data permit or if considered appropriate, terminal elimination half-life ($t_{1/2}$) will be estimated. Descriptive statistics will be provided for these PK parameters in tabular form (N, mean, SD, CV, median, minimum, maximum, geometric mean and its associated CV) by dose, cycle, and day.

Individual patient and median profiles of the concentration-time data will be plotted by dose, cycle, and day using nominal times. Median profiles will be presented on both linear-linear and log-linear scales.

Graphs of PK concentration over time and tables of PK parameters will be provided by Cullinan.

7.11 Pharmacodynamic EBV DNA

A line graph for mean +/- SD of change from baseline for EBV DNA will be provided by visit for all post baseline visits (C1D14, C2D0, C2D14, C3D0) for Phase 1 Dose Escalation. EBV DNA population will be used to generate this graph.

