# Pharmacodynamic EBV DNA

Summaries of change from baseline to treatment to post-treatment levels of cell-free plasma EBV DNA will be provided, as appropriate. Individual values and descriptive statistics (N, mean, SD, minimum, maximum, geometric mean and its associated CV) will be presented by dose and cycle in tabular form. The rate of partial response (a reduction by 3xlog10 or more) or complete response (reduction below the LLOD of the assay) will be computed as well.

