4.2 Secondary Endpoints

Phase 1:

- The rate and severity of treatment emergent AEs at the MTD and BCAD.
- Single dose and steady state plasma pharmacokinetic parameters of VK 2019.
- Incidence of safety laboratory assessment abnormalities
- Incidence of abnormalities in vital signs or other clinical safety assessments
- ORR, DOR, and Disease control rate (DCR) per RECIST v1.1
- Rate of partial or complete plasma EBV DNA antiviral response during treatment (assessed as 3xlog¹⁰ reduction or a drop below the lower limit of detection of the assay [LLOD], respectively).

Phase 2a:

- The rate and severity of treatment emergent AEs at the MTD, BCAD, and RP2D.
- Rate of partial or complete plasma EBV DNA antiviral response during treatment (assessed as 3xlog¹⁰ reduction or a drop below the lower limit of detection of the assay [LLOD], respectively).
- Plasma PK parameters of VK-2019.

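### SAP 7.11 plans only a mean ± SD change plot for EBV DNA, with no scale, dose split or LLOD rule, and gives the three-log/LLOD response rate no output

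*SAP*

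**What the plan says.** - SAP 7.11 has one output, "A line graph for mean +/- SD of change from baseline for EBV DNA will be provided by visit", produced "for all post baseline visits (C1D14, C2D0, C2D14, C3D0) for Phase 1 Dose Escalation". It says nothing about scale, transformation, dose grouping, individual values or results below LLOD.
- SAP 7.1 sets the default summary for continuous variables, unless otherwise noted, as "arithmetic mean (mean), standard deviation (SD), median, minimum, and maximum".
- SAP 4.2 keeps as a secondary endpoint, for both Phase 1 and Phase 2a: "Rate of partial or complete plasma EBV DNA antiviral response during treatment". Partial response is a three-log10 reduction; complete response is a drop below LLOD.
- Protocol section 14, Pharmacodynamic EBV DNA, plans "Individual values and descriptive statistics (N, mean, SD, minimum, maximum, geometric mean and its associated CV) will be presented by dose and cycle". It also says that this will be computed: "The rate of partial response (a reduction by 3xlog10 or more) or complete response (reduction below the LLOD of the assay".
- For pharmacokinetics, SAP 7.10 names geometric means, presentation by dose, individual profiles and a log axis ("Median profiles will be presented on both linear-linear and log-linear scales"). SAP 7.11 has nothing comparable.

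**The concern.** The endpoint is defined by fold reduction and detectability. The only planned display, on its default reading, averages absolute changes. If loads differ by orders of magnitude, an absolute-change average follows the highest-load patients, and SD bars summarise a skewed quantity poorly. With no dose split, the graph also cannot show whether any fall depends on dose.

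The graph is the only EBV DNA output the SAP describes for the Phase 1 anti-EBV secondary objective. It could mislead about typical patients, and the report could contain no estimate of the endpoint itself.

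**Working it through.** **1. Planned outputs side by side**

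| Element | Protocol section 14 | SAP 7.11 |
|---|---|---|
| Three-log/LLOD response rate | To be computed | Absent, though kept as an endpoint in SAP 4.2 |
| Individual values | Yes | Absent |
| Geometric mean and CV | Yes, beside arithmetic mean and SD | Absent |
| By dose | Yes | Not stated |
| Change from baseline | Yes, scale not named | Mean ± SD plot, scale not named |

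No other SAP section fills the gap. SAP 7.4 only counts the EBV DNA population. SAP 7.14.2 concerns laboratory safety values and does not name EBV DNA.

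**2. Can loads plausibly span orders of magnitude?** Inclusion criterion 3 admits patients with more than 4,000 genomes per µg plasma DNA and no upper limit, or with EBV-positive tissue and no plasma minimum. A three-log fall that stays detectable requires a baseline above 1,000 × LLOD. The endpoint therefore allows for loads three orders of magnitude above LLOD, alongside patients who may enter with little or none. A three-log responder starting at 4,000 contributes 4 − 4,000 = −3,996 to the raw sum. A patient at an assumed 1,000,000 contributes about as much by drifting 0.4%.

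**3. Fixed example (assumed values).** Baselines are 1,000; 2,000; 5,000; 10,000; 20,000; 1,000,000. The first five fall three logs and the last rises 1.5-fold.
- Raw: the falls sum to 999 + 1,998 + 4,995 + 9,990 + 19,980 = 37,962. Mean change = (500,000 − 37,962)/6 = **+77,006** (SD 207,340).
- Log10: (5 × (−3) + 0.176)/6 = **−2.47**.
- In the reverse case, where five double and the last halves, raw mean = (38,000 − 500,000)/6 = −77,000 and log10 mean = (5 × 0.301 − 0.301)/6 = +0.20.

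**4. Simulation (20,000 datasets per setting).** Assumptions: log10 baseline normal with SD 0.75–1.25; log10 change c normal with mean m and SD 0.4, independent of baseline. Patient i's raw change is Dᵢ = Bᵢ(10^cᵢ − 1), where Bᵢ is the baseline load. The top patient's share is max|Dᵢ| / Σ|Dᵢ|.

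Top patient's median share at m = −0.3:
- n=6: 57–73% raw, against about 33% on log10.
- n=20: 37–56% raw, against about 13% on log10.
- n=30 (the planned escalation size in SAP section 5): 32–51% raw.

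Share of trials in which the mean shows a rise:
- m = −0.3, raw: 18–22% at n=6 and n=20; 17–20% at n=30. At n=6, about 14% of all trials had a raw rise while most patients fell.
- m = −0.3, log10: about 3.3% at n=6, 0.05% at n=20, almost never at n=30.
- m = −1.0, raw: at most about 0.3% at n=6 and 0.2% at n=20.

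**5. Why the sign result depends on effect size.** The expected fold change on the raw scale is 10^(m + (ln 10/2) × 0.4²) = 10^(m + 0.184). At m = −0.3 this is 10^(−0.116) = 0.77, an expected 23% fall although the typical patient halves. At m = −1.0 it is 10^(−0.816) = 0.15, far enough from 1 to keep the sign stable.

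**6. Other settings.** With mean change 0 and change SD 0.5, the two largest changes carry 91% (n=6) and 67% (n=30) of the raw total at baseline SD 1.0, against 59% and 18% on log10. At baseline SD 0.3 and n=30 the raw share is 40%. Dominance is weaker when spread is narrow and n larger, but does not vanish.

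**The case against.** The best case for the plan has five parts.

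- **Scale and pooling are not written.** A reader might infer that the SAP states a raw-scale, pooled analysis. It does not: an arithmetic mean of log10 change would fit the wording, and 7.11 is silent on dose. This stands, so the raw scale and lack of a dose split are a reading of 7.11 through 7.1, not a stated choice. It remains the natural reading, because 7.10 names log scales and dose grouping where they are wanted. If log10 is intended, the same edit is needed.
- **The protocol lists arithmetic mean and SD too.** A reader might infer that the protocol treats EBV DNA as purely log-distributed. Its list puts arithmetic mean and SD beside the geometric mean, and complete response is a detectability criterion. Mean ± SD is therefore a protocol-listed statistic; the fault is using it alone.
- **The size depends on assumptions.** A mean change of −0.3 log10 is one tenth of the endpoint threshold, and at −1.0 log10 wrong-direction means nearly disappear. This stands.
- **The scope is limited.** The SAP serves an abbreviated report, the protocol plans no confirmatory inference, and no stated dose or stopping rule uses this graph. This limits the stakes. It does not explain the omission, since SAP 7.5, 7.12 and 7.15 say expressly when outputs are dropped and 7.11 does not.
- **Laboratory listings might carry the values.** The protocol's Lab Assessments table includes EBV DNA. SAP 7.14.2 is nevertheless written for safety values, and even a listing would give neither geometric means nor a response rate.

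**Conclusion.** The concern holds as under-specification with a poor default, together with an endpoint that has no output. The firmest part needs no assumptions: the three-log/LLOD response rate is retained in SAP 4.2 and required by the protocol, yet SAP 7 plans no output for it, and the protocol's individual values and geometric means by dose and cycle are also missing.

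The scale problem is conditional. On the default reading a few high-load patients can dominate the curve. The risk of a wrong-direction mean is material if the true effect is small, and negligible at about −1.0 log10 under the same spread. A reader might infer that one or two patients will decide the curve; the documents do not support that, because they give no EBV DNA distribution and a share of 32% at n=30 is a minority. Confidence is medium. The point is worth correcting, but it concerns a descriptive secondary output.

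**What to change.** Amend SAP 7.11 as follows:

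1. Plot mean ± SD of log10 change from baseline, or the geometric mean ratio, with individual patient lines by dose.
2. State the rule for values below LLOD (for example, set to LLOD) and flag those points. Show patients with baseline below LLOD separately: with that substitution, a patient who stays undetectable has a change of zero, which is uninformative.
3. Add a table of the three-log/LLOD response rate by dose with its denominator stated, or say that it is omitted from the abbreviated report.

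Cost: a few lines of SAP text, a log transform and one small table. No new data are needed.
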